## Brief overview of analytic methods.

Feasibility will be assessed by examining accrual rates, attrition rates, adherence to the study protocol, hardware/software issues, and use of the intervention (e.g., frequency and duration of visits, number of educational video views). A feasibility questionnaire will be administered at the end of the intervention to CGs and to patients (if alive).

To measure potential efficacy, we will use mixed models (MMs) to analyze specific outcomes (i.e., symptoms, CG burden, hospitalization, etc.). MMs do not assume that each subject will contribute data at all-time points and so they can be used for data with complex attrition patterns. In these models, the subject's initial status (intercept) and the change in their status (slope) will be treated as random effects. The variables of group, time, the interaction of group and time, and any variable that differs between the two conditions at baseline or other variables of theoretical interest, expectation for inclusion in models from the literature, or near significance of difference by conditions will be modeled as fixed effects. Nurses will be examined in models as levels of a random classification factor. For all variables, four models will be tested: a linear effect of time, a log-linear effect of time allowing for more rapid change at the beginning of the study, a quadratic effect of time with no random slope for the quadratic term, and a quadratic effect of time with the slope of the quadratic term also being allowed to be random. Model selection will be done using the Bayesian Information Criterion, a measure of model misfit with a penalty added for extra parameters, with inferences only being made from the best fitting model. We will also test for a random intercept and random effect of time by hospice nurse to control potentially for nesting by nurse. Given the small number of hospice nurses we anticipate to be involved in the study, we do not expect either random effect to be statistically significant and plan to drop it from the model if it is not. We will also test for effects in CGs who are bereaved very early in the study.

Mixed model analysis will be conducted on seven outcomes.

For post-test power assessment, the selection of 100 patient–CG dyads is based on power calculations with an all-cause attrition rate on not filling out post-test assessments of 10%, leaving 90 dyads. For post-test comparisons of post-intervention measures under a two-tailed hypothesis, we will have 80% power to detect a group-by-time interaction with an effect size of  $d=0.66$ , which is regarded as a medium-large effect size. A data collection protocol whereby data are collected at baseline and in weeks 1, 2, 3, 4, 5, and 6 would correspond to 7 measurements for subjects who complete the 6-week intervention/pilot test. To conduct a power-analysis we conducted a simulation to model attrition directly. We assumed everyone would have at least 1 measurement after hospice discharge, including patients who died during week 1 of the intervention. The mortality rate modeled using samples drawn from data on 1,000 home hospice patients was 35% at four weeks, 62% at eight weeks, and 72% at twelve weeks. This means we would have 7 measurements on approximately 28% of the data.

Our power to detect effects will depend largely, on how quickly the intervention is successful. With two time points for each subject we will have 80% power to detect an effect size of  $d=0.57$  on any outcome, which is considered a moderate effect. If it takes the full 7 time points for the full effect of the intervention to be realized our power will be reduced and we will require a large effect ( $d=0.8$ ) to obtain 80% power. A 25% reduction in burden reported by family CGs corresponds to an effect size of 0.71. Under a two-tailed hypothesis test, if the intervention is successful by week 1, we would have 94% power to detect an effect of this size. We would have 70% power for a two-tailed hypothesis test across 7 time points.

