### **Aim 3: I-HoME pilot RCT**

For Aim 3, 100 CGs will be recruited from VNS Health hospice teams. The intervention will be randomized by nurse. Therefore, CGs of certain nurses will receive the I-HoME intervention (n=50) for up to six weeks while others will be recruited to receive standard home hospice care (n=50). Feasibility and potential efficacy measures will be administered at baseline and after each visit/weekly (timeline may change based on results obtained from Aim 2). Baseline measures will be collected during the in-home visit or via phone call by the research team and subsequent measures will be collected via phone call or electronic survey.

**Intervention.** CGs randomized to the intervention group will have access to live synchronous video visits with a research nurse interventionist on a scheduled (weekly) and as-needed basis (hours will be dependent on funding). The study team will either make an in-home visit or conduct a phone call with the CG (based on CG preference) at the start of the study to obtain consent and train the CG on the I-HoME intervention. This group will be educated about I-HoME and learn how to use the tablet to access videos and communicate with the interventionist. Participants will also be given a laminated user guide/help card and have access to technical assistance if hardware or software concerns arise or if an adverse event occurs. Software by Doxy.me will be used to conduct HIPAA compliant synchronous video visits. Participants in this study will continue to receive standard home hospice care in addition to the I-HoME intervention. Phone visits will be conducted if video visits are unable to be done due to hardware or software issues.

**Standard Care Control.** Participants in the standard care control group will receive home hospice services as usual. They will also receive a tablet with hospice resources. These participants will complete the same measures as participants in the intervention condition on the same timeline using identical assessment procedures.

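### The efficacy model treats the baseline score as an outcome and tests group-by-time, which is less precise than adjusting the weekly scores for baseline

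*Combined protocol and SAP*

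**What the plan says.** All the modelling text is in Brief overview of analytic methods. The fixed effects start with "The variables of group, time, the interaction of group and time". For the random part, "the subject's initial status (intercept) and the change in their status (slope) will be treated as random effects". Other covariates enter if they differ, or nearly differ, between arms at baseline, or on grounds of theory or literature. The baseline value of the outcome is not named among them. Time may be linear, log-linear or quadratic (two versions), with the form chosen by BIC. Nurse random effects are dropped if not significant.

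The power text states that "we will have 80% power to detect a group-by-time interaction with an effect size of" d = 0.66, after an "all-cause attrition rate on not filling out post-test assessments of 10%, leaving 90 dyads". It counts baseline plus weeks 1 to 6 as seven measurements. The Aim 3 section says that efficacy measures are given at baseline and then weekly. It also says "The intervention will be randomized by nurse".

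Nowhere does the plan prespecify the baseline score as a covariate, or a common baseline mean for the two arms.

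**The concern.** With baseline in the outcome vector and a free group term, the interaction measures how far the arms move apart from wherever each one started. With two time points that is a comparison of change scores, which carries the full measurement noise of the baseline score. Regressing follow-up on baseline removes only the part of baseline that predicts follow-up. When the arms have the same expected baseline, it estimates the same effect with smaller variance. The trial has 100 caregivers and many early deaths, and the plan reports only 70% power across seven time points for a 25% reduction in burden. Precision available from data already collected is therefore worth having.

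The covariate rule adds a secondary risk. If baseline burden happened to differ between arms, the rule could bring the baseline score in as a covariate while it is still an outcome row in the same model.

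**Working it through.** **Inputs from the plan.** 100 dyads, 50 per arm; 90 after 10% attrition (45 per arm); two-tailed test; 80% power; d = 0.66 for the interaction; mortality 35% at 4 weeks and 62% at 8 weeks; at least one post-baseline score for everyone.

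**Assumed, not in the plan.** Two-sided alpha 0.05; correlation r of 0.4 to 0.6; slope variance s of 0 to 0.02 per week², in units of the baseline variance and independent of the intercept; no nurse clustering.

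**1. The plan's own figure.** A plain comparison of 45 with 45 detects d = (1.960 + 0.842) × √(2/45) = 0.59 (0.597 with the t distribution), and power at 0.66 is 87%. So 0.66 does not follow from the stated inputs alone. A change-score contrast would give it at r = 0.39: 0.597 × √(2 × 0.61) = 0.66. So would a variance inflation of 1.25 (0.591 × √1.25 = 0.66), or alpha 0.025 with t (0.659). The plan does not say which, so 0.66 cannot be used to recover r.

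**2. Two time points.** The variance factor is 2(1 − r) for change and 1 − r² for baseline adjustment. The ratio is (1 + r)/2, which is below 1 for every r below 1.

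| r | ratio | detectable d, change | detectable d, adjusted |
|---|---|---|---|
| 0.4 | 0.70 | 0.597√1.2 = 0.65 | 0.597√0.84 = 0.55 |
| 0.5 | 0.75 | 0.597√1.0 = 0.60 | 0.597√0.75 = 0.52 |
| 0.6 | 0.80 | 0.597√0.8 = 0.53 | 0.597√0.64 = 0.48 |

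This shows the direction. The planned analysis has up to seven time points, so the size has to come from step 3.

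**3. The weekly schedule.** Linear interpolation of the stated mortality gives 91%, 83%, 74%, 65%, 58% and 52% alive at weeks 1 to 6. The covariance of a caregiver's scores is V = r·11ᵀ + s·ttᵀ + (1 − r)·I, and generalised least squares was applied with 50 per arm.

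- Planned model: rows from week 0 to the last week; terms 1, t, group, group × t. The week 6 effect is 6 × the interaction.
- Adjusted model: rows from week 1 to the last week, with V reduced by r² in every cell (conditioning on baseline); same terms. The week 6 effect is group + 6 × the interaction.
- Log time: t is replaced by log(1 + t) in the fixed effects of both models, with the random slope still per week.

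Variance ratio, adjusted to planned, for the week 6 difference:

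| r | linear, s = 0 / 0.01 / 0.02 | log, s = 0 / 0.01 / 0.02 |
|---|---|---|
| 0.4 | 0.76 / 0.82 / 0.86 | 0.68 / 0.77 / 0.83 |
| 0.5 | 0.81 / 0.86 / 0.89 | 0.74 / 0.82 / 0.88 |
| 0.6 | 0.86 / 0.90 / 0.92 | 0.80 / 0.88 / 0.93 |

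The reduction is 8–24% under linear time and 7–32% under log time. Since √0.92 = 0.96 and √0.76 = 0.87, the detectable effect under linear time shrinks by about 4% to 13%.

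**4. The choice of contrast matters.** Over the same grid, with baseline as covariate:

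- Week 6 with week as a category: ratio 1.14 to 1.35 against the planned linear model, and up to 1.43 against log. This is less precise, because only about half the caregivers are expected at week 6 and nothing is borrowed from earlier weeks.
- Average over weeks 1–6: ratio 0.96 to 1.33 against the average implied by the planned linear model, so no reliable gain; 0.71 to 0.90 against log.

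The quadratic forms were not computed.

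**The case against.** The strongest reply is that the free group term is deliberate and sound. Nurses are randomised. Caregivers are recruited afterwards, and the nurse first confirms that contact is appropriate (recruitment procedures, Aim 3). The same section concedes that some differences cannot be controlled. If the arms differ systematically at baseline, baseline adjustment and change from baseline estimate different quantities, each resting on an assumption the data cannot check. This stands. A reader might infer that using baseline as a covariate, rather than imposing equal means, removes the difficulty; it does not. It is the reason to keep the interaction model as a sensitivity analysis.

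Second, a growth-curve interaction is a standard, valid analysis, and baseline enters its likelihood. A reader might infer that the baseline score is wasted; it is used, but inefficiently.

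Third, the two-point table might suggest that the detectable effect would fall from 0.66 to 0.55, or that the trial needs 25–43% more caregivers than necessary (1/0.80 and 1/0.70). The documents support neither figure: r is not given, 0.66 has other explanations, and the analysis is not limited to two time points. The plan's own two-time-point figure is already d = 0.57.

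Fourth, the gain can nearly vanish. In the closely related model with a common baseline mean, allowing intercept–slope correlations of −0.3 to 0.3, r up to 0.7 and slope SD up to 0.15 per week, the variance ratio ran from 0.71 to 1.00 under linear time.

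Finally, the recruitment text makes feasibility the primary aim, and section B of the monitoring plan says this is not an efficacy trial. That limits the weight of the point but does not remove it, since potential efficacy is part of Aim 3.

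**Conclusion.** The point holds as a modest efficiency improvement to a valid analysis. The structure is plain in the text: baseline is an outcome, the group difference at baseline is free, the interaction is what is powered, and the baseline score is not a prespecified covariate. With the plan's parametric time form kept, adjusting for baseline cuts the week 6 variance by about 8–24% (linear) or 7–32% (log). Those ranges rest on assumed r of 0.4 to 0.6, slope variance of 0 to 0.02 independent of the intercept, interpolated mortality, equal expected baselines and no nurse clustering. They do not extend to a categorical-week contrast, which loses precision, or to the weeks 1–6 average, which gives no reliable gain over the linear model.

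The point covers only outcomes scored at baseline and weekly. Hospitalization, and satisfaction recorded at the final interview, have no baseline score to adjust for.

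**What to change.** In Brief overview of analytic methods, for outcomes scored at baseline and weekly (such as burden, depression, anxiety and symptoms):

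1. Use the week 1–6 scores as the outcome and the caregiver's own baseline score as a prespecified covariate. Add group, time and group-by-time in the plan's parametric time form, not week as a category. Keep the nurse effect.
2. Name one contrast, the group difference at week 6.
3. Keep the planned interaction model as a sensitivity analysis, and explain any disagreement in terms of baseline differences that may arise because recruitment follows nurse randomisation.
4. State that a baseline score never enters one model both as an outcome row and as a covariate.
5. Align Table 2 with the text. The table lists burden, depression and anxiety only as post-intervention measures, while the Aim 3 text has the measures given at baseline too.

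The cost is wording; no participant, visit or measurement is added. The one drawback is that a caregiver without a baseline score is excluded or needs that value imputed.

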**Measurements.** All participants will be assessed on the measures listed in Table 2 (see **Appendix B** for more details). Measures will be administered at baseline and in weeks 1, 2, 3, 4, 5 and 6. Validated surveys will be administered via phone by a research assistant. Post-visit measures for caregivers will be collected during each interview, and additional measures will be collected during the final interview. Participants will be compensated \$50 for an initial baseline survey followed by \$25 (by ClinCard) each time they complete a within study phone call/electronic survey. Post-intervention measures for patients will be collected from their medical chart in both groups. For the intervention group, the collection will start from study enrollment to 4 weeks after the final I-HoME intervention visit or the date of program end (which ever one is earlier). For the control group, the collection will start from study enrollment to 11 weeks after enrollment.

Table 2.

Baseline measures		Post-intervention measures	
Patient (from medical chart)	Caregiver	Caregiver	Patient
Age	Age	Burden	Hospice discharge reason
Gender	Gender	Depression	Use of non-home hospice services (inpatient care, respite care)
Race/ethnicity	Race/ethnicity	Anxiety	Number of nursing visits
DNI/DNR status	Religion	Software issues	Number of social work visits
Medications	Education	Hardware issues	Number of chaplain visits
Comorbidities	Relationship to patient	Patient symptoms	
Hospice diagnosis	Hours providing care to patient	CaSES	
	Number of CGs caring for the patient	Caregiver (Final Interview)	
	Occupation	CG Satisfaction	
	Income	Feasibility questionnaire	

### Addition of patient participants for Aim 3

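### Covariates may enter the efficacy models because the arms differ, or nearly differ, at baseline; a short prognostic list should be named beforehand instead

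*Combined protocol and SAP*

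**What the plan says.** The section Brief overview of analytic methods specifies mixed models in which "the subject's initial status (intercept) and the change in their status (slope) will be treated as random effects". Group, time and their interaction are fixed effects. The same sentence opens four further routes for covariates, joined by the word or:

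- an observed baseline difference: "any variable that differs between the two conditions at baseline";
- theory, and the literature: "other variables of theoretical interest, expectation for inclusion in models from the literature";
- a near miss on a test between arms: "near significance of difference by conditions will be modeled as fixed effects".

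No test or cut-off defines a difference or a near miss, and no covariate is named under any route. The section adds that "Mixed model analysis will be conducted on seven outcomes", without listing them.

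Candidate variables are in Table 2, under Aim 3: I-HoME pilot RCT: 7 patient items and 10 caregiver items at baseline. The same paragraph says of the measures: "Measures will be administered at baseline and in weeks 1, 2, 3, 4, 5 and 6". In Table 2, however, caregiver satisfaction belongs to the final interview, and discharge reason and use of inpatient or respite care are post-intervention items taken from the chart.

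**The concern.** Whether a variable differs between randomised arms says nothing about whether it predicts the outcome. A rule based on observed difference can admit an irrelevant variable that happens to be imbalanced. It can also pass over a prognostic one whose imbalance is moderate but not significant. The theory and literature routes could bring prognostic variables in, but with no names given they can be filled in after the data have been seen by arm.

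Two things are at stake. The first is that the adjusted estimate should come from a model that could have been written down beforehand. The second is the precision that a fixed prognostic covariate gives. Both matter most where an outcome is measured once and the arm comparison is direct. If a logistic model were used for a binary outcome such as live discharge, changing the covariates would also change the odds ratio being estimated.

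**Working it through.** **Inputs.** From the documents: 17 baseline variables (Table 2, by count: 7 + 10); 100 dyads, 50 per arm, 90 after 10% attrition (power paragraphs of the analytic overview); two teams of 5 to 7 nurses, so 10 to 14 nurses (recruitment procedures, Aim 3). Assumed, because the documents give no value: two-sided alpha 0.05; p<0.05 for a difference and p<0.10 for a near miss; independent baseline tests; nurse intraclass correlation (ICC) 0.05; covariate-outcome correlation 0.3 to 0.7.

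**1. The plan's own figures.** None is attached to the covariate rule. The early-effect power figures reproduce with 50 per arm and no attrition, using power = Φ(d√(n/2) − 1.96):

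- d=0.71: 0.71 × 5 − 1.96 = 1.59, power 94.4% (94.0% by t), stated 94%.
- d=0.57: 0.57 × 5 − 1.96 = 0.89, power 81.3% (80.6% by t), stated 80%.

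With 45 per arm, the effect detectable with 80% power in a simple comparison is (1.960 + 0.842)/√22.5 = 0.59. Step 4 uses this value. The plan's d=0.66 for 90 dyads concerns a group-by-time test that depends on an unstated within-person correlation. It is not disputed here.

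**2. Flags by chance.** For k=17 independent tests at level a, the expected number is ka and the chance of at least one is 1 − (1 − a)^k.

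- p<0.05: 17 × 0.05 = 0.85 expected; 1 − 0.95^17 = 58%.
- p<0.10: 17 × 0.10 = 1.7 expected; 1 − 0.90^17 = 83%.

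A prognostic variable not named under the theory or literature routes would enter by the imbalance routes in only 5% to 10% of trials.

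**3. Allowing for nurses.** If the baseline tests ignore clustering, the design effect is 1 + (m − 1) × ICC, and the true flag rate is 2P(Z > z/√deff), where z is the critical value of the test.

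- 10 nurses: m=10, deff = 1 + 9 × 0.05 = 1.45; flag rates 10.4% and 17.2%.
- 14 nurses: m=7.14, deff = 1 + 6.14 × 0.05 = 1.31; flag rates 8.6% and 15.0%.

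The 5% to 10% range becomes about 9% to 17%.

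**4. Effect on a single end-point comparison.** 10,000 simulated trials per setting, 45 per arm, one covariate, continuous outcome, individual allocation. The rule adjusts only if the baseline p-value is below 0.10.

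| Correlation | Power at d=0.59: none / rule / prespecified | Type I error: none / rule / prespecified |
|---|---|---|
| 0.3 | 79.1% / 79.6% / 82.2% | 5.1% / 4.7% / 4.8% |
| 0.5 | 78.8% / 80.3% / 88.2% | 5.1% / 4.1% / 4.9% |
| 0.7 | 79.0% / 82.6% / 97.5% | 4.9% / 3.1% / 4.9% |

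The rule recovers little of the available precision. Its type I error falls below nominal because a covariate left out when balanced still inflates the residual variance, although it then adds little to the difference between arms.

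**5. Effect on the group-by-time test.** A main-effect covariate mostly explains the intercept. In 60 simulated trials of 90 subjects with 2 to 7 visits (assumed variances; covariate correlated 0.5 with the random intercept; a few fits gave convergence warnings), adding it multiplied the group-by-time standard error by 0.9995. Only the standard error of the group main effect fell, by about 10%.

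**The case against.** The strongest reply is that the rule is wider than its imbalance routes. Theory and literature variables are admitted whatever their balance, and that is how prognostic variables would normally come in. This stands. A reader might infer that most prognostic variables are left out, but the documents do not support that: the 5% to 17% entry rates describe the imbalance routes alone. What remains is that an unnamed list is not fixed in advance.

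Three other stronger readings also fail.

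- **Imbalance is pure chance.** Allocation is by nurse, the nurse is asked whether contact with the caregiver is appropriate, and the Aim 3 recruitment section concedes that some differences cannot be controlled. Imbalance may partly reflect recruitment. That is a reason to look at it, and a better reason to fix prognostic covariates beforehand.
- **False positives are inflated.** Selection uses baseline data, not outcomes, and step 4 shows a conservative test.
- **Imbalance gives each outcome its own model.** A Table 2 variable that differs between arms does so whichever outcome is analysed. Only the theory and literature routes could vary by outcome.

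It is also fair to say that this is a pilot. The safety plan's interim-analysis section calls it a feasibility and not an efficacy trial. Even so, potential efficacy is a stated aim, and power is given for two-tailed tests. Pilot status lowers the priority but does not justify the rule.

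**Conclusion.** The point holds in a limited form. Observed differences between arms decide part of each efficacy model, no threshold is given, and the remaining routes name nothing. Prespecification would give a more transparent model. In the illustrated single end-point setting it would also raise power from about 80% to 88% at an assumed correlation of 0.5 (from 79.6% to 82.2% at 0.3, and from 82.6% to 97.5% at 0.7).

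That gain applies mainly to outcomes measured once. The safety plan's Specific Aims list seven efficacy outcomes, plausibly the seven to be modelled: symptoms, burden, depression, anxiety, satisfaction, live discharge and hospitalization. Table 2 indicates that satisfaction is collected only at the end, and that the discharge and service-use items come from the chart after enrolment. The simulation used a continuous outcome, so its figures carry over only approximately to binary ones. For the group-by-time test of repeated outcomes the gain is very small if covariates enter as main effects. The plan does not say whether covariate-by-time terms are intended.

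The chance-flag figures rest on the assumed thresholds and on independence between baseline variables. The clustered figures rest also on the assumed ICC. This is a cheap improvement, not a flaw that invalidates the trial.

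**What to change.** - Delete the two routes that depend on a difference or near difference between arms.
- Before arms are compared, name two or three prognostic covariates already in Table 2 (for example hospice diagnosis, relationship to patient, hours providing care) and use them in every model.
- Keep any adjustment prompted by observed imbalance as a labelled sensitivity analysis.
- For repeated outcomes, baseline is already one of the seven measurements. Keep it as a response and do not also enter it as a covariate.
- Add hospice team only after reconciling the Aim 3 and recruitment sections (allocation by nurse) with the safety plan's Brief Description of Project Design (allocation by hospice team), and only if allocation is confirmed to be by nurse within team. If whole teams were allocated, team would be confounded with arm.

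The cost is one paragraph of wording and a few degrees of freedom. No new data are needed.

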**Aim 3:** For the pilot RCT, I will be collaborating with VNS Health home hospice teams (each team consists of 5-7 nurses). These two teams will be randomized to receive the intervention (I-HoME) or standard care at the nursing level. Since this is a pilot study and the primary aim is to assess for intervention feasibility, we acknowledge that we will not be able to control for certain differences. We will work with VNS Health hospice leadership to select hospice teams that serve similar patient populations. In both hospice teams, family CGs will be screened for study eligibility within 7 days of their home hospice admission through chart review. Screening will be conducted regularly by the research team. Prior to reaching out to potential participants, the

research team will contact the nurse caring for the patient and CG to confirm that it would be appropriate to contact the CG for the study. Weill Cornell and VNS Health are co-engaging one or more research staff through a subaward – they will be hired by VNS Health and performing the initial screening/recruitment. VNS Health staff will contact subjects by phone to inquire about their interest in participating (see telephone script C and D). If there is interest expressed by the CG over the phone, a research team member will reach out to conduct an in-home visit to describe the study and obtain written informed consent.

No external investigators (unless they are a VNSNY employee or VNSNY volunteer/intern) will be given names or contact information until subject approval is obtained through a VNSNY provider.

Hospice patients (n=20) will be referred by caregivers that are enrolled in the study. The study team will ask the caregiver (after they have been consented) if the patient would be open to participating in the study to provide ratings on their symptoms. Patients with a hospice diagnosis of dementia not be considered for the study. Eligible patients will be contacted by phone by a research team member.

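### Nurses are randomised in Aim 3, but the nurse effects leave the efficacy models if not significant, which 10 to 14 nurses cannot justify

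*Combined protocol and SAP*

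**What the plan says.** The section on Aim 3 (pilot RCT) states: "The intervention will be randomized by nurse". The Aim 3 paragraph under the procedures for recruiting study subjects agrees: "These two teams will be randomized to receive the intervention (I-HoME) or standard care at the nursing level". It puts each team at 5–7 nurses, so two teams give about 10–14 nurses, or 5–7 per arm, if all take part.

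The overview of analytic methods plans mixed models for potential efficacy: "Mixed model analysis will be conducted on seven outcomes". Nurse enters as a random factor, and a nurse random intercept and a nurse-by-time effect are each tested. The plan points to the low number of nurses as its reason, and the rule then reads: "we do not expect either random effect to be statistically significant and plan to drop it from the model if it is not". Nothing is specified in place of the dropped terms: no small-sample method, robust variance or nurse-level analysis.

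The power paragraphs in the same section state no ICC, design effect or number of nurses.

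**The concern.** The nurse term is in the model because nurses were randomised. Its place should not depend on a test with little power. The plan's reason for expecting non-significance is that nurses are few. That explains why the test would miss clustering; it is not evidence that clustering is absent.

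Which nurse term matters depends on the outcome. For weekly measures (burden, depression, anxiety, symptoms), the group-by-time test needs the nurse-by-time term. For outcomes measured once, the group comparison needs the nurse intercept. These include satisfaction ("additional measures will be collected during the final interview") and chart data ("Post-intervention measures for patients will be collected from their medical chart in both groups").

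If an outcome clusters by nurse and the relevant term is dropped, the interval for the I-HoME effect is too narrow. A difference between nurses could then be read as an effect of the intervention.

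**Working it through.** **Inputs.** From the documents: 100 caregivers (50 per arm), 90 after 10% attrition, two teams of 5–7 nurses, two-tailed tests. Assumed: level 0.05 (none is stated), ICC 0 to 0.20, k = 10, 12 or 14 nurses, near-equal caseloads.

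**1. The plan's own power figures.** For n independent caregivers the noncentrality is d·√(n/4), on n − 2 df.
- d = 0.57, n = 100: 0.57 × 5 = 2.85, power 80.6% (plan: 80%).
- d = 0.71, n = 100: 0.71 × 5 = 3.55, power 94.0% (plan: 94%).

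Both match independent caregivers with no design effect. This is inferred from the match, since the plan describes a simulation without full inputs. The seven-time-point figures were not rebuilt.

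**2. Chance of detecting a real nurse effect** (one score per caregiver, n = 90). The F statistic for nurse within arm has k − 2 and 90 − k df and is scaled by 1 + m·ICC/(1 − ICC), with m = 90/k.
- k = 10, ICC 0.05: scale 1 + 9 × 0.05/0.95 = 1.474, critical value 2.056, detection 21%.
- k = 14, ICC 0.05: scale 1.338, critical value 1.882, detection 18%.

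**3. False positives under test-then-drop.** Null trials, 100,000 per setting. If the F-test is significant, nurse means are compared on k − 2 df; otherwise a pooled t-test on 88 df is used. Ranges cover k = 10 to 14.

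| ICC | Nurse term significant | False positives, drop rule |
|---|---|---|
| 0 | about 5% | 4.8% |
| 0.01 | about 7% | 5.3–5.4% |
| 0.02 | 9–10% | 5.8–6.4% |
| 0.05 | 18–21% | 6.9–7.8% |
| 0.10 | 38–42% | 8.1–9.1% |
| 0.20 | 73–75% | 7.4–8.0% |

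A nurse-level t-test stays at 4.9–5.1% throughout. Among trials in which the term was dropped, the rate is 8.3–9.8% at ICC 0.05 and 12.1–15.1% at ICC 0.10. At ICC 0.20 the test usually finds the clustering, so the inflation stops growing. Discharge and hospitalization events were not simulated.

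**4. Repeated-measures check.** 20,000 trials per setting: 100 caregivers, baseline plus weekly to week 6, the plan's mortality (35% at four weeks, 62% at eight). Assumed: residual variance 1, slope variance 0.04 or 0.2, caregiver variances known. The nurse slope is tested by likelihood ratio at 0.05; the nurse intercept and BIC selection are left out. About 50% of caregivers then have all seven measurements. A rerun used the plan's figure: "This means we would have 7 measurements on approximately 28% of the data".

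| Nurse share of slope variance | False positives | Rerun with 28% |
|---|---|---|
| 0 | 4.4–4.8% | 4.4–4.9% |
| 5% | 5.3–6.7% | 5.0–6.1% |
| 10% | 6.1–8.1% | 5.7–7.6% |

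**5. Power with nurse as the unit** (n = 100). The design effect is DE = 1 + (n/k − 1)·ICC, the noncentrality is divided by √DE, and df = k − 2. Example: k = 10, ICC 0.05, d = 0.71 gives DE = 1 + 9 × 0.05 = 1.45 and 3.55/√1.45 = 2.95 on 8 df, so power is 73%.

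| ICC | d = 0.57 | d = 0.71 |
|---|---|---|
| 0 | 70–74% | 87–90% |
| 0.02 | 63–70% | 82–87% |
| 0.05 | 55–63% | 73–81% |

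**6. The d = 0.66 figure.** Ninety independent caregivers would detect 0.597 at 80% power. With nurse-based df, 90 caregivers detect 0.64–0.68 at ICC 0, 0.66–0.70 at ICC 0.01 and 0.73–0.80 at ICC 0.05. So 0.66 is compatible with very low clustering on that basis. Its inputs are not given, and it is not called wrong.

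**The case against.** The strongest reply is that little hangs on this. The recruitment section makes feasibility the primary aim and accepts that some differences cannot be controlled. The interim-analysis section says this is not an efficacy trial. No stated decision rests on an efficacy p-value. Seven outcomes without multiplicity control would already give 1 − 0.95⁷ = 30% for at least one false positive if they were independent. One to three further points per test adds little to an exploratory reading. This stands as a limit on severity. It does not make a too-narrow interval acceptable, because the plan still models and powers two-tailed efficacy comparisons.

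Clustering may also be small. A separate research nurse delivers I-HoME, and the check closest to the planned model shows the smaller inflation. Both points stand for caregiver mood. They carry less weight for chart outcomes such as nursing visits and inpatient or respite use, where differences between hospice nurses are plausible. The rule does keep nurse when it is detected, so the harm arises only when the term is dropped.

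The d = 0.66 figure might already contain an allowance. It implies a variance inflation of (0.66/0.597)² = 1.22. With ordinary df that is an ICC of 0.222/8 = 0.028 for 10 nurses, or 0.222/5.43 = 0.041 for 14. The documents support neither reading over the other.

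Finally, two nurse variance components in four time models with 10–14 nurses may not converge, and keeping them is conservative when clustering is absent. Both are true, so a fallback must be written down.

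**Conclusion.** The concern holds, and the rule should be changed. As written, it can remove the randomised unit from the efficacy models on the strength of a test that misses an ICC of 0.05 about four times in five. At assumed ICCs of 0.05–0.10 the false-positive rate is roughly 7–9% with one score per caregiver. With repeated measures it is roughly 5–8% when nurses hold 5–10% of slope variance. At ICC 0 there is no inflation, and at 0.01 it is slight.

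The logical fault does not depend on the ICC; the size of the harm does. The figures also assume a 5% level, 10–14 participating nurses and near-equal caseloads. With an assumed spread of 1–14 caregivers per nurse over 14 nurses, the drop rule gave 8.7–10.7%. The feasibility results are unaffected.

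**What to change.** Delete the drop rule and write the following into the analysis section:

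- Keep the nurse terms in every Aim 3 efficacy model, including all four time models compared by BIC, whatever their p-values. Use a nurse intercept and nurse-by-time effect for weekly outcomes, and a nurse intercept for outcomes measured once.
- Test group or group-by-time with small-sample degrees of freedom based on the number of nurses.
- If a model does not converge, simplify the nurse terms first, keeping nurse-by-time for group-by-time tests. If it still fails, compare nurse-level means of one pre-specified summary on number of nurses minus 2 df. For weekly outcomes, use each caregiver's estimated slope weighted by its precision, because follow-up is unequal. For outcomes measured once, use the score. In the check, weighted slopes gave 4.7–5.4% false positives. Unweighted slopes also held the level but lost much power (20–22% against 56–64% in one setting).
- Restate the d = 0.57 and 94% power figures over an assumed ICC range with the number of nurses, and give the inputs to d = 0.66.

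**Cost.** Conduct, sample and data collection do not change. With 90 caregivers, power at d = 0.71 goes from about 90% under the drop rule to 84–87% for a nurse-level test at ICC 0, and from 79–84% to 71–78% at ICC 0.05. Without clustering, keeping the terms is conservative: 3.2–3.6% false positives with one score, 1.5–2.4% in the repeated-measures check.

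A lighter option raises the drop threshold to 0.20. It gives 5.4–6.2% at ICC 0.05–0.10 and costs less power. It still discards the randomised unit in some trials, and gave 6.9–7.5% with the uneven caseloads above.

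Separately, the project-design summary in the Data and Safety Monitoring Plan assigns by hospice team. It must be reconciled with assignment by nurse elsewhere. If two whole teams were the assigned units, nurse terms would not repair the analysis.
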